# 9.7. Prior and Concomitant Therapy

All non-study medications, including prescription, over-the-counter, or herbal therapies, used by the subject will be documented for the 30 days prior to Screening and throughout the study. The Investigator will determine if the prior/concomitant medication(s) affect the subject's eligibility to participate or continue to participate in the study. The following restrictions on concomitant medications will be in place during the study:

- Opioid receptors are likely to be occupied by BPN, which may reduce the analgesic effects of an opioid. The dissociation of BPN from the receptors may take up to 2 weeks following the last CAM2038 q1w injection. Therefore, subjects requiring analgesic emergency treatment or anesthesia for surgery should ideally be treated with a non-opioid analgesic. Opioids may be used with caution, but as higher doses may be required for analgesic effect, there may be a higher potential for toxicity with opioid administration. The clinical course should be carefully evaluated and fully documented for subjects who have a requirement for any opioid analgesic for >7 days continually or general anesthesia for surgery within 2 weeks of the final dose of CAM2038 q1w.
- Buprenorphine is metabolized via CYP3A4. Because CYP3A4 inhibitors may increase plasma concentrations of BPN, if CYP3A4 inhibitors such as azole antifungals (e.g., ketoconazole), macrolide antibiotics (e.g., erythromycin), and HIV protease inhibitors (e.g., ritonavir, indinavir, and saquinavir) are required, the Medical Monitor must be consulted. Interactions with CYP3A4 inducers have not been investigated; therefore, it is recommended that the use of agents such as phenobarbital, carbamazepine, phenytoin and rifampicin be avoided in subjects receiving study treatment. The Medical Monitor must be consulted prior to starting subjects on any of these agents.
- Concomitant use of other narcotic anesthetics, benzodiazepines, phenothiazines, other tranquilizers, or other central nervous system (CNS) depressants (including alcohol and sedative/hypnotics) may cause respiratory and CNS depression. Use of these substances should be minimized during treatment with CAM2038. If these sedatives are required during the study, the Medical Monitor must be consulted. Subjects should be advised of the danger of concomitant use of sedatives while participating in in the study.
- Ancillary medications (PRNs) will be allowed as needed throughout the study (see Table 5), with the exception of Hydromorphone Challenge Session days starting from midnight (i.e., approximately 9 hours prior to dosing) through to the end of the Hydromorphone Challenge Session (i.e., approximately 5 hours after dosing). Once the session has ended, PRNs will be permitted. Ancillary medications will also not be permitted from midnight on Day -1 (i.e., approximately 9 hours prior to dosing) until after administration of the first dose of CAM2038 on Day 0.

Version: 2.0, 17NOV2015 Page 53 of 99

Table 5 Ancillary Medications (PRNs) for Relief of Withdrawal Symptoms

Symptom	Treatment	Dose	Route of Administration	Dosing Schedule
Anxiety/restlessness	hydroxyzine	50-100 mg	Oral	Q6H, PRN
Diarrhea	bismuth subsalicylate (e.g., Pepto-Bismol®)	30 mL	Oral	Q4H, PRN
Hypotension/sedation	clonidine	0.1 mg	Oral	Q6H, PRN
Insomnia	Zolpidem (i.e., Ambien®)	5 mL	Oral	PRN
Musculoskeletal pain/general body	acetaminophen (e.g., Tylenol®)	650 mL	Oral	QID, PRN
aches/discomfort	ibuprofen	400 mg	Oral	Q4-6H, PRN
Nausea/dyspepsia	alumina, magnesia, simethicone	30 mL	Oral	QID, PRN
Vomiting/severe nausea	promethazine	25 mg	Oral or IM	Q3-4H, PRN

IM=intramuscular; PRN=as needed; QID=4 times/daily; Q3-4H= every 3 to 4 hours; Q4H=every 4 hours; Q4-6=every 4 to 6 hours; Q6H=every 6 hours

On a case-by-case basis, the Investigator is permitted to allow the use of some additional concomitant medications not outlined in Table 5 Error! Reference source not found., for example, to treat an AE, as long as the Investigator determines that the medication will not affect the subject's safety or study integrity (e.g., topical medications). Whenever possible, the Investigator should obtain approval from the sponsor's Medical Monitor prior to administering the medication.

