#### 10.4.11. Objective Opioid Withdrawal Scale (OOWS)

The Objective Opioid Withdrawal Scale (OOWS) contains 13 physically observable signs, rated present or absent, based on a timed period of observation of the patient by a rater (Appendix 17.3; Handelsmen et. al. 1987).

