# 10.6. Additional Safety Measures and Withdrawal

#### 10.6.1. Opioid Effects

Buprenorphine and hydromorphone can produce the typical side effect profile of mu opioid agonists, and these may include nausea, vomiting, headache, dry mouth, itchiness, drowsiness, sweating, dizziness, stimulation, somnolence, lightheadedness, restlessness, a feeling of well-being, talkativeness, urinary retention and constipation. More serious side effects may include allergic reaction and respiratory depression. However, subjects will be opioid-dependent and, thus, familiar with these common side effects, and not likely to experience the severe side effects such as allergic reaction.

Physiological and behavioral effects, as well as the emergence of possible side effects, will be monitored daily during Hydromorphone Challenge Sessions. Subjects who exhibit hypersensitivity (i.e., experience a SAE) following administration of any of the drugs will be excluded from further research participation. Heart rate, blood pressure, oxygen saturation and respiratory rate will be monitored frequently throughout sessions. However, if a subject experiences an allergic reaction, diphenhydramine will be available for oral administration.

While the risk of significant respiratory depression may be decreased in opioid-dependent individuals (due to greater tolerance), standardized criteria for nursing staff and research personnel will be employed during the monitoring of individuals. If respiratory rate drops below 12 breaths/min accompanied by sedation, subjects will be prompted verbally to breathe. This approach of physical and verbal stimulation is often sufficient to prompt breathing and restore a normal respiratory rate. Subjects will be monitored carefully with a watch-and-wait approach and will be accompanied continuously by nursing personnel and evaluated by the staff physician. If clinical evaluation determines that a subject's level of sedation is increasing, naloxone will be promptly administered parenterally to produce immediate reversal of the hydromorphone effects. Naltrexone will also be available if longer blockade is necessary.

The study will be conducted in CRUs with trained nursing staff available on site. A crash-cart with naloxone will be on site as well. Emergency response will be available by a physician codeteam if needed.

Version: 2.0, 17NOV2015 Page 65 of 99

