#### 10.6.2. Treating Opioid Withdrawal

If opioid withdrawal occurs after dosing with CAM2038 q1w (precipitated withdrawal), the following assessments will be collected every 4 hours while the subject is awake for at least 24 hours after dosing to include:

- 1) COWS,
- 2) OOWS,
- 3) VAS assessment of opioid withdrawal severity.

Treatment will be based upon clinical judgment of the medically responsible physician at each site. To ensure the safety of subjects, incidences of precipitated withdrawal in response to CAM2038 q1w will be followed carefully and an amendment of the protocol to ensure subjects are in a more advanced state of opioid withdrawal e.g., increase required COWS score from 8 to 12, to reduce the risk of BPN-related precipitated withdrawal, will be considered if more than one incidence occurs.

Ancillary medications that will be made available for symptomatic relief of all episodes of withdrawal (precipitated by CAM2038 q1w and other) are summarized in Table 5Error!

Reference source not found. Error! Reference source not found.

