symptoms or allergies	Total Score
0 not present	
I nasal stuffiness or unusually moist eyes	The total score is the sum of all 11 items
2 nose running or tearing	Initials of person
4 nose constantly running or tears streaming down cheeks	completing assessment:

Score: 5-12 = mild; 13-24 = moderate; 25-36 = moderately severe; more than 36 = severe withdrawal

259

This version may be copied and used clinically.

Journal of Psychoactive Drugs

Volume 35 (2), April - June 2003

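### Three cells of Protocol Table 5 need correcting: the symptom label on the clonidine row and the units for zolpidem and acetaminophen

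*Protocol*

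**What the plan says.** Table 5 sits in Protocol Section 9.7 and is titled as a list of as-needed drugs for withdrawal symptoms. It names eight drugs against seven symptom labels. The clonidine row reads "Hypotension/sedation clonidine 0.1 mg Oral Q6H, PRN". The acetaminophen row, for musculoskeletal pain and body aches, ends "650 mL Oral QID, PRN". Zolpidem, for insomnia, is given as 5 mL by mouth as needed.

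The text just above the table sets the timing. The drugs are allowed as needed throughout the study, "with the exception of Hydromorphone Challenge Session days starting from midnight (i.e., approximately 9 hours prior to dosing) through to the end" of the session, about 5 hours after the injection. Then: "Once the session has ended, PRNs will be permitted". A similar closure applies from midnight before the first CAM2038 dose until it is given.

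Two other sections bear on the table. Section 10.6.1, on opioid effects, lists drowsiness and somnolence among the effects of mu agonists. It says that if clinical evaluation finds that a subject's "level of sedation is increasing, naloxone will be promptly administered parenterally to produce immediate reversal of the hydromorphone effects". Section 10.6.2, on treating withdrawal, points back to Table 5: "Ancillary medications that will be made available for symptomatic relief of all episodes of withdrawal (precipitated by CAM2038 q1w and other").

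**The concern.** Table 5 is the written list from which site staff would order as-needed drugs, so its cells work as instructions. The clonidine row names no sign of withdrawal. As written, it is triggered by two signs that could follow a hydromorphone dose of up to 18 mg given on top of depot buprenorphine, and the table reopens when the session ends, about 5 hours after that dose. A subject who is still drowsy or has low blood pressure at that point matches the row.

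That clonidine lowers blood pressure and can sedate is general pharmacology and is not stated in the protocol. The internal evidence is that the protocol itself classes drowsiness as an agonist effect, so the label does not fit a withdrawal table.

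The zolpidem and acetaminophen entries cannot be followed as written. What is at stake is subject safety and a clean instruction to sites. The efficacy result is not at stake.

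**Working it through.** No power, alpha or sample-size figure bears on this point. The check compares texts and does some simple arithmetic.

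**Clonidine label against the withdrawal scales.** The inputs are Protocol Appendices 17.2 and 17.3 and Section 10.4.11. For COWS, "The total score is the sum of all 11 items". OOWS "contains 13 physically observable signs, rated present or absent". That makes 11 + 13 = 24 item lines. The two scales share several signs (yawning, tremor, restlessness and anxiety among them), so these are not 24 distinct signs. None of the lines is hypotension or sedation.

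Of the seven symptom labels in Table 5, five correspond to something on COWS: anxiety/restlessness, diarrhea, musculoskeletal pain, nausea and vomiting. Two do not: insomnia and hypotension/sedation. Absence from the scales is therefore not proof that a label is wrong. What separates the clonidine label from insomnia is that Section 10.6.1 places drowsiness and somnolence on the opposite side, as effects of the opioid.

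**Units in Table 5.**

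| Drug | Dose as written | Assessment |
|---|---|---|
| Hydroxyzine | 50-100 mg | plausible |
| Bismuth subsalicylate | 30 mL | plausible, liquid |
| Clonidine | 0.1 mg | unit plausible, label in question |
| Zolpidem | 5 mL | apparent unit error |
| Acetaminophen | 650 mL four times daily | apparent unit error |
| Ibuprofen | 400 mg | plausible |
| Alumina, magnesia, simethicone | 30 mL | plausible, liquid |
| Promethazine | 25 mg | plausible |

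Four of the eight drugs are in mL, and two of those four look wrong. Acetaminophen as written comes to 650 mL x 4 = 2,600 mL a day.

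**Timing of the closed window.** Midnight to a 9:00 am injection is 9 h, and the session adds 5 h, so the window is 9 + 5 = 14 h. The Drug Liking ratings that define Emax (SAP 9.1.1) run to 300 minutes, and 300 / 60 = 5 h, so the window covers all of them.

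After a 9:00 am depot injection, the following midnight is hour 15 (24 - 9), and the session ends at 2:00 pm, hour 29 (15 + 14). Section 10.6.2 asks for withdrawal assessments for at least 24 h after the depot if precipitated withdrawal occurs. The last 24 - 15 = 9 h of that minimum fall inside the closed window. Section 10.6.2 does not repeat the closure, which is why a cross-reference would help.

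**The case against.** The strongest reply is that the table's title already limits it to withdrawal. No prescriber would give clonidine to a hypotensive subject or pour 650 mL of acetaminophen. Other safeguards also exist. Section 9.7 requires consultation with the Medical Monitor for sedatives and other CNS depressants. Section 10.4.7 allows monitoring beyond 5 hours when needed. Section 10.6.2 leaves treatment of withdrawal to the site physician. Sections 7.1.4 and 10.4.5.2 require a safety review before the next hydromorphone dose. Most of this stands and is why the point is minor. It does not make the three cells right, and the review before the next hydromorphone dose does not govern which as-needed drug is chosen when a session ends.

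A reader might infer more than the documents support:

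- **That Table 5 and Section 10.6.1 prescribe rival treatments for one sign.** They address different situations: 10.6.1 deals with hydromorphone over-effect and gives naloxone only when sedation is increasing. It gives no treatment for hypotension, so nothing there conflicts with that half of the label.
- **That Section 10.6.2 overrides the challenge-day closure.** It refers the reader to Table 5, which sits directly beneath the closure in 9.7. Leaving a rule unrepeated does not set a different rule.
- **That every mL dose is wrong, or that the unit errors set 9.7 against 10.6.** Only two of the four look wrong, and both are faults within the table.
- **That a number of harmed subjects can be given.** The documents do not say how often sedation or hypotension lasts to the end of a session, so any count would rest on an invented rate.

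**Conclusion.** The point holds as a minor subject-safety text correction. Its size is three cells in one table: one symptom label and two units. No effect on the primary analysis is claimed, since under 9.7 the as-needed drugs are closed for the whole period in which Drug Liking is rated on challenge days.

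The conclusion on clonidine rests on the protocol's own classing of drowsiness as an opioid effect, on the absence of both signs from the two scales as supporting evidence, and on general pharmacology for the blood-pressure half of the label. The withdrawal sign that the sponsor meant cannot be recovered from the documents. The conclusion on units assumes that the sponsor meant milligrams, which the sponsor should confirm.

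**What to change.** In Table 5:

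1. Replace the symptom label on the clonidine row with the withdrawal sign the sponsor intended.
2. Add a footnote to that row: clonidine is not given to a sedated or hypotensive subject; sedation after hydromorphone is managed under Section 10.6.1; hypotension is evaluated by the physician. The last clause is needed because 10.6.1 contains no management of hypotension.
3. Change zolpidem to 5 mg and acetaminophen to 650 mg once the sponsor confirms them. Leave the two 30 mL liquids as they are.

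Optionally, add one sentence to Section 10.6.2 saying that use of Table 5 follows the timing in Section 9.7. That sentence should not create a rescue exception inside the closed window or a rule for withholding hydromorphone. An exception would allow rescue drugs during the ratings that define Emax. A withheld dose would leave a missing Emax, and SAP 9.1.3 does not impute missing scores.

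The cost is three cells, one footnote and at most one sentence. No new data are needed and the primary model does not change.

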# 9.8. Treatment Compliance

Study drugs will be administered by study personnel, thus no subject compliance procedures are necessary.

Version: 2.0, 17NOV2015 Page 54 of 99

#### 10. STUDY PROCEDURES AND ASSESSMENTS

All study assessments will be performed at the visits and time points outlined in the Schedule of Assessments (Table 4); the following sections outline the details and procedures associated with the assessments.

# 10.1. Demographics and Other Baseline Characteristics

#### 10.1.1. Informed Consent

The nature of the study and its risks and benefits will be explained to the subject by the Investigator or designated study personnel. The subject must voluntarily provide written informed consent on an ethics-approved ICF, prior to performing any study-related procedures. The subject's medical records must document that the consent process has been completed and that written informed consent has been obtained from the subject prior to the initiation of any study-specific procedures. Documentation that the subject was given adequate time to ask the Investigator (or designee) questions about their participation in the study and that a signed and dated copy of the ICF was provided to the subject should also be included in the medical records or clinical chart.

#### 10.1.2. Demographics

The following demographics will be recorded: age (birthdate), sex, race, and ethnicity. A complete psychosocial history will be obtained including: education, employment status, marital/significant other status, residential status and legal status/arrest history.

#### **10.1.3.** Medical History

The complete medical history will include histories of acute, chronic, or infectious disease; surgical or oncologic histories; and any reported conditions affecting major body systems that have occurred within the last five years or that the Investigator deems clinically significant that should be included in the subject's medical history. All findings on medical history will be evaluated by the Investigator for clinical significance. Medical histories will be obtained according to the site's standard operating procedures.

### **10.1.4. Medication History**

All medications (prescription and non-prescription, herbal medications/natural health products, or investigational drugs) taken by the subjects during the 30 days prior to Screening will be recorded in the source documentation as medication history. Substance Abuse History and Treatment History (Section 10.1.5) will be collected separately and stored in the subject's file.

## 10.1.5. Substance Use and Treatment History

A complete history of previous and current illicit drug use, substance abuse/dependence, and treatments for any substance use disorders (pharmacologic as well as non-pharmacologic) will be obtained. This will include drugs used, type, frequency and patterns of abuse, routes of administration, doses, and drug preferences, using a timeline follow-back type of interview (Fals-Stewart et al., 2000).

Version: 2.0, 17NOV2015 Page 55 of 99

## **10.1.6.** Contraceptive Requirements

Female subjects of childbearing potential must be using and willing to continue using medically acceptable contraception during the study. Examples of medically acceptable forms of contraception include true abstinence, hormonal contraceptives (combined oral pill, patch or vaginal ring, intrauterine device or system, progestin implant or injection), bilateral tubal ligation, or double-barrier methods (e.g., male condom with spermicide in addition to a diaphragm or a contraceptive sponge).

Female subjects of non-childbearing potential are not required to use contraception and to undergo pregnancy tests; however, they must have documentation supporting that they are surgically sterile (hysterectomy and/or bilateral oophorectomy/salpingo-oophorectomy, as determined by subject medical history) or congenitally sterile, or must be post-menopausal. Post-menopausal is defined as being amenorrheic for at least 2 years without another cause or amenorrheic for at least 1 year without another cause and a documented FSH level ≥50 mIU/mL.

Male subjects with female partners of childbearing potential must agree to use a medically acceptable method of contraception from Screening Visit through at least 3 months after the last dose of study drug. Male subjects must also agree not to donate sperm during the study through at least 3 months after the last dose of study drug.

# 10.2. Eligibility Review

Prior to receiving the first dose of hydromorphone on Day -3, subjects must meet all inclusion and not meet any exclusion criteria as outlined in Sections 8.1 and 8.2.

The Investigator or designee must document that the subjects meet each individual criterion via a signed note or eligibility and clinical stability checklist during Screening. Signatures on these documents must be dated on or before the date of Day -10.

# 10.3. Pharmacodynamic Assessments

All subjects will undergo a scripted training and practice regimen prior to completion of the paper and pen subjective measures as outlined in Table 6.

Testing conditions for pharmacodynamic assessments should remain as consistent as possible throughout the Treatment Phase. Subjects will be monitored carefully to ensure that they are completing the pharmacodynamic assessments appropriately. Study staff are encouraged to provide additional subject training as needed, to ensure that the subjects comprehend the differences between different types of VASs. Training dates/times will be documented in the subject's files. Subject training can only occur before VAS administration or after the 5 hour Challenge session is completed. The training script will be provided to the sites.

#### 10.3.1. Visual Analog Scales

Each VAS will be scored as an integer from 0 to 100. When appropriate, VASs will be administered as bipolar measures, meaning that the neutral point equals 50 (i.e., Drug Liking and Alertness/Drowsiness VAS). The neutral point will also be labeled with an anchor, such as

Version: 2.0, 17NOV2015 Page 56 of 99

"neither like nor dislike." Unipolar VASs (i.e., High, Good, Bad, and Any Effects VAS) are presented with anchors such as "not at all" (score = 0) to "extremely" (score = 100), where the neutral point equals 0. The use of a unipolar or bipolar scale is determined by the nature of the subjective effect being measured.

If precipitated withdrawal occurs after administration of CAM2038 q1w, subjects will be requested to complete a unipolar VAS assessment of opioid withdrawal severity.

Table 6 lists the subjective effects VAS question text and response anchors.

**Table 6** Visual Analog Scale Descriptions

Scale Interpretation	Description	Question Text	Response Anchors		
Balance	nce Drug Liking At this moment, my		0: Strong disliking 50: Neither like nor dislike 100: Strong liking		
Other effects	Any Drug Effects	At this moment, I feel any drug effects			
Positive	High	At this moment, I feel high			
Positive	Good Drug Effects	At this moment, I feel good drug effects	0: Not at all 100: Extremely		
Negative	Bad Drug Effects	At this moment, I feel bad drug effects			
Other Effects	Desire to use opioids	At this moment, I desire opioids	0: Definitely not 100: Definitely so		
Other Effects	Alertness/Drowsiness	At this moment, my mental state is	0: Very drowsy 50: Neither drowsy nor alert 100: Very alert		
Other Effects	Opioid Withdrawal Severity  I feel opioid withdrawal		0: Not at all 100: Extremely		

